11.1.2 Serious Adverse Event (SAE)

An SAE is an adverse event that:

- Results in death. NOTE: Death due to disease progression should not be reported as a SAE, unless it is attributable by the site investigator to the study drug(s)
- Is life-threatening (defined as an event in which the subject was at risk of death at the time of the event; it does not refer to an event which hypothetically might have caused death if it were more severe)
- Requires inpatient hospitalization for >24 hours or prolongation of existing hospitalization. **NOTE:** Hospitalization for anticipated or protocol specified procedures such as administration of chemotherapy, central line insertion, metastasis interventional therapy, resection of primary tumor, or elective surgery, will not be considered serious adverse events.
- Results in persistent or significant disability/incapacity
- Is a congenital anomaly or birth defect
- Is an important medical event (defined as a medical event(s) that may not be immediately life-threatening or result in death or hospitalization but, based upon appropriate medical and scientific judgment, may jeopardize the subject or may require intervention (e.g., medical, surgical) to prevent one of the other serious outcomes listed in the definition above). Examples of such events include, but are not limited to, intensive treatment in an emergency room or at home for allergic bronchospasm; blood dyscrasias or convulsions not resulting in hospitalization; or the development of drug dependency or drug abuse.

11.1.3 Unexpected Adverse Event

For this study, an AE is considered unexpected when it varies in nature, intensity or frequency from information provided in the current IB, package insert, or when it is not included in the informed consent document as a potential risk. Unexpected also refers to AEs that are mentioned in the IB as occurring with a class of drugs or are anticipated from the pharmacological properties of the drug, but are not specifically mentioned as occurring with the particular drug under investigation.

11.1.4 Relatedness

AEs will be categorized according to the likelihood that they are related to the study drug(s).

To ensure consistency of AE and SAE causality assessments, site investigators should apply the following general guideline:

Yes

There is a plausible temporal relationship between the onset of the AE and administration of ipatasertib, and the AE cannot be readily explained by the subject's clinical state, inter-current illness, or concomitant therapies; and/or the AE follows a known pattern of response to ipatasertib; and/or the AE abates or resolves upon discontinuation of atezolizumab or dose reduction and, if applicable, reappears upon re- challenge.

No

Evidence exists that the AE has an etiology other than the ipatasertib (e.g., preexisting medical condition, underlying disease, inter-current illness, or concomitant medication); and/or the AE has no plausible temporal relationship to ipatasertib administration (e.g., cancer diagnosed 2 days after first dose of Ipatasertib).

Expected adverse events are those adverse events that are listed or characterized in the current Investigator Brochure (IB).

Unexpected adverse events are those not listed in the current IB or not identified. This includes adverse events for which the specificity or severity is not consistent with the description in the package insert or IB.

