11.2.3 Serious Adverse Events (SAEs)

11.2.3.1 Site Requirements for Reporting SAEs to Big Ten CRC Administrative Headquarters

- SAEs will be reported from time of study drug administration until 30 days after discontinuation of study drug(s) or until a new anti-cancer treatment starts, whichever occurs first.
- SAEs will be reported on the SAE Submission Form and entered in the SAE tab in the EDC system.
- SAEs include events related and unrelated to the study drug(s).
- All SAEs will be recorded in the subject's medical record and on the appropriate study specific eCRF form within the EDC system.
- All SAEs regardless of relation to study drug will be followed until resolution to \leq Grade 1 or baseline and/or deemed clinically insignificant and/or until a new anti-cancer treatment starts, whichever occurs first.

For SAEs and AESIs assessed as at least possibly related to the study drug(s) or assessed as unknown relation, the site will submit the completed SAE Submission Form (see Documents/Info tab in the EDC) to Big Ten CRC AHQ within **1 business day** of discovery of the event. The form will be sent electronically to Big Ten CRC AHQ at [contact]. The site investigator is responsible for informing the IRB and/or other local regulatory bodies of the SAE as per local requirements.

The original copy of the SAE Submission Form and the email correspondence must be kept within the study file at the study site.

Once the SAE has resolved, sites must electronically submit a follow up SAE Submission Form within a reasonable timeframe to Big Ten CRC AHQ at [contact].

SAEs assessed as unrelated to study drug will entered in to the EDC within 30 days of awareness of the event.

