11.2.3.3 Big Ten CRC AHQ Requirements for Reporting SAEs or Pregnancies to Bayer

Upon receipt of an SAE Submission Form or Pregnancy Reporting Form from the site, Big Ten CRC AHQ will report to Bayer within **24 hours** of receipt of the SAE Reporting Form/ Pregnancy Reporting Form from a site. Follow-up information will be provided to Bayer HealthCare Oncology as it is received from a site.

SAE Reports will be sent to the email address provided below. By sending to this e-mail address, the Bayer Pharmacovigilance group and the Bayer clinical operations project manager will receive copies of the reports. This process will be tested and established before the first patient is enrolled in the trial.

Bayer Safety Contacts:

[contact]

For e-mail transmission of individual SAE reports: [contact]

SAEs assessed as unrelated to study drug will be reported to Bayer on a monthly basis.

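### Section 11.1.4 gives relatedness criteria for ipatasertib only, with a dechallenge test on a drug outside the regimen, so an SAE attributed to darolutamide alone could be filed as unrelated and reported late

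*Combined protocol and SAP*

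**What the plan says.** The opening line of 11.1.4 makes the study drugs, in the plural, the object of the causality judgement. The guideline that follows is the only set of causality criteria in the document, and sites are told to apply it for consistency.

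- **Yes, timing:** "There is a plausible temporal relationship between the onset of the AE and administration of ipatasertib", with no ready alternative explanation.
- **Yes, known pattern:** "the AE follows a known pattern of response to ipatasertib".
- **Yes, dechallenge:** "the AE abates or resolves upon discontinuation of atezolizumab or dose reduction".
- **No:** "Evidence exists that the AE has an etiology other than the ipatasertib", or timing that is implausible for ipatasertib.

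Section 5 gives the regimen as androgen deprivation, darolutamide and ipatasertib. Atezolizumab appears nowhere else in the document. Darolutamide is not named in 11.1.4.

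The label sets the reporting route. Section 11.2.3.1 applies the 1-business-day deadline to this group: "For SAEs and AESIs assessed as at least possibly related to the study drug(s) or assessed as unknown relation". For the rest, "SAEs assessed as unrelated to study drug will entered in to the EDC within 30 days of awareness of the event". Section 11.2.3.3 has the Big Ten CRC Administrative Headquarters (AHQ) forward a received form to the darolutamide supplier within 24 hours, but "SAEs assessed as unrelated to study drug will be reported to Bayer on a monthly basis".

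**The concern.** The criteria cover one of the two oral study drugs. An investigator who attributes an SAE to darolutamide and not to ipatasertib has found a cause other than ipatasertib, and that is the wording of the No category. The dechallenge limb, as written, gives no help for either drug.

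At stake is how fast a serious event reaches AHQ and the company whose drug is suspected. Section 5 says that this combination had not been evaluated before, so prompt reporting matters for both agents. AHQ also handles the 7 and 15 Day Reports to FDA (11.2.3.5) and cannot act on an event that it has not yet received.

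**Working it through.** No statistical figure is involved. The check follows one event through the text and then compares the causality scales.

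**Step 1: an example.** Section 10.2.6 lists ischemic heart disease and heart failure for darolutamide. The short list for ipatasertib in 10.1.6 contains neither, although it is not exhaustive and refers to the Investigator's Brochure. Take a hospitalization of more than 24 hours for heart failure, which is an SAE under 11.1.2, and suppose that the investigator attributes it to darolutamide and not to ipatasertib.

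**Step 2: apply 11.1.4 literally.**
- Timing limb of Yes: it asks about ipatasertib and requires that no other explanation is ready. The investigator has one.
- Pattern limb of Yes: not on the protocol's ipatasertib list.
- Dechallenge limb of Yes: it names stopping a drug that the patient never took.
- No: there is evidence of a cause other than ipatasertib. The wording fits.

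**Step 3: follow the label.**

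| Reporting step | Related or unknown | Unrelated | Source |
|---|---|---|---|
| Site to AHQ | 1 business day | EDC entry within 30 days | 11.2.3.1 |
| AHQ to darolutamide supplier | 24 hours from form receipt | monthly | 11.2.3.3 |

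The document does not say how the 30-day entry and the monthly report line up. If a full monthly cycle, assumed to be 28 to 31 days, follows an entry made on day 30, the supplier hears at 30 + 28 = 58 to 30 + 31 = 61 days after site awareness. The related route takes 1 business day plus 24 hours.

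**Step 4: look for a safeguard.** Under 11.2.3.4 the sponsor-investigator assesses relatedness again. That review works from a summary that AHQ sends after the site's form arrives, so it can correct the label but cannot recover the time lost at the site.

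**Step 5: compare the scales.**
- 11.1.4: Yes or No.
- 11.2.3.1: at least possibly related, unknown, or unrelated.
- 12.7.2: possible, probable or definite relation to ipatasertib.

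Consider an event with plausible timing that an intercurrent illness could readily explain, with no firm evidence either way and no known ipatasertib pattern. It does not meet the timing or pattern limb of Yes, and it does not meet No. Yet a possible relation is expedited under 11.2.3.1, and a possible relation to ipatasertib makes the event ipatasertib-related for the stop in 12.7.2. A Yes/No record does not map onto either section.

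**The case against.** The best defence is that the text calls itself a general guideline and that its governing sentence covers all the study drugs. So does the expedited trigger in 11.2.3.1, which also takes in events of unknown relation. The examples under No are other illnesses and concomitant medication. Darolutamide is study treatment (5.3), handled apart from concomitant medication (5.4). The 24-hour route to the darolutamide supplier shows that darolutamide-related reports were expected. The Yes limbs are joined by and/or, so the stray drug name does not block a Yes. Both drugs are normally taken daily, so timing alone will rarely exclude ipatasertib, and rash and fatigue are listed for both.

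Much of this stands. A careful site could call the event related, and the SAEs at risk are those that an investigator assigns to darolutamide and not to ipatasertib. The accurate statement is that such an event could be classed No, not that it will be. But the defence relies on sites overriding the written criteria, and the examples under No do not limit its general wording.

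A reader might infer more than the text supports:

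- **Phase I decisions.** The DLT definition in 5.1.1 has its own attribution test, which excludes only events clearly due to the underlying disease or extraneous causes. A darolutamide toxicity that meets the criteria counts whatever is recorded under 11.1.4.
- **Phase II safety stop.** Section 12.7.2 counts only prolonged surgical delays due to ipatasertib-related events. An event due to darolutamide alone is outside it by design. Only the mismatch of scales touches this rule.
- **Agent-specific decisions in 6.3.1.8.** These rest on investigator discretion and do not refer to 11.1.4.
- **Follow-up.** SAEs are followed regardless of relation (11.2.3.1). Events of grade 2 or higher, and SAEs, ongoing at the safety visit are followed without a relatedness condition (7.1). All AEs are recorded in any case (11.2.1).

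**Conclusion.** The wording is wrong as it stands and should be corrected. Section 11.1.4 promises a judgement on all the study drugs, gives criteria for one, and tests dechallenge on a drug outside the trial.

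The consequence is limited to reporting time. For an SAE attributed to darolutamide alone and classed No, the site's limit moves from 1 business day to 30 days, and the supplier's from 24 hours after form receipt to monthly. The 58 to 61 day total rests on the assumed full monthly cycle after a day-30 entry. How many SAEs would be affected cannot be estimated, because the document gives no rate for events attributed to darolutamide alone. The conclusion also assumes that sites apply the guideline literally. The AE and SAE forms are not in the document and may already ask about each drug.

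The mismatch of scales is a separate, smaller fault and holds whichever drug is suspected. Neither fault changes the primary endpoint, the sample size or the grade 3 and 4 toxicity endpoint.

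**What to change.** Four changes to the text:

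1. In 11.1.4, state the Yes and No criteria for each study drug, ipatasertib and darolutamide.
2. In the dechallenge criterion, replace atezolizumab with the study drug being assessed.
3. State that relation to any study drug counts as related for 11.2.3.1 to 11.2.3.3.
4. Use one causality scale in 11.1.4, 11.2.3.1 and 12.7.2, and say where possible and unknown relation fall.

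The cost is wording and, if the AE form does not already record causality by drug, one extra field. A separate causality category for the combination is not needed.

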11.1.5 AEs of Special Interest (AESIs)

AEs of Special Interest are defined as a potential safety problem, identified as a result of safety monitoring of the Product. AESIs shall be forwarded to Genentech as described in the Genentech Safety Data Exchange Agreement (SDEA).

The Ipatasertib Events of Special Interest are:

- Cases of potential drug-induced liver injury that include an elevated ALT or AST in combination with either an elevated bilirubin or clinical jaundice, as defined by Hy's Law
- Suspected transmission of an infectious agent by the study drug, as defined below
Any organism, virus, or infectious particle (e.g., prion protein transmitting transmissible spongiform encephalopathy), pathogenic or non-pathogenic, is considered an infectious agent. A transmission of an infectious agent may be suspected from clinical symptoms or laboratory findings that indicate an infection in a patient exposed to a medicinal product. This term applies only when a contamination of the study drug is suspected.
- Grade \geq 3 fasting hyperglycemia
- Grade \geq 3 hepatotoxicity
- Grade \geq 3 ALT/AST elevations
- Grade \geq 2 colitis/enterocolitis
- Grade \geq 3 diarrhea
- Grade \geq 3 rash
- Grade \geq 2 pneumonitis

11.1.6 Selected Adverse Events

Additional data including grade, timing and required interventions will be collected for the following selected adverse events:

- Diarrhea
- Asthenia (fatigue)
- Nausea
- Neutropenia (neutrophil count decreased, febrile neutropenia)
- Rash (e.g., maculopapular, erythema, urticarial, dermatitis, rash popular, skin exfoliation, toxic skin eruption)
- Erythema multiforme
- Vomiting
- Oral mucositis (stomatitis, mucosal inflammation, mouth inflammation, mouth ulceration)
- Hyperlipidemia (hypercholesterolemia, hypertriglyceridemia, hyperlipidemia, blood cholesterol increased, blood triglycerides increased)
- Hepatotoxicity (ALT, AST increased)
- Hyperglycemia (blood glucose increased)

- Pneumonitis (interstitial lung diseases)

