10. Any of the following within 6 months before registration: stroke, myocardial infarction, severe/unstable anginal pectoris, coronary/peripheral artery bypass graft, congestive heart failure New York Heart Association (NYHA) class III or IV.
11. Congenital long QT syndrome or QTcF $>$ 480 milliseconds
12. Grade \geq 2 uncontrolled or untreated hypercholesterolemia (>300 mg/dL) or hypertriglyceridemia (>300 mg/dL)
13. History of or active IBD or active bowel inflammation (diverticulitis)
14. Lung disease: pneumonitis, interstitial lung disease, idiopathic pulmonary fibrosis, cystic fibrosis, Aspergillosis, active tuberculosis, or history of opportunistic infections (pneumocystis pneumonia or cytomegalovirus pneumonia)
15. Treatment with strong CYP3A inhibitors or strong CYP3A inducers within 2 weeks or 5 drug-elimination half-lives, whichever is longer, prior to initiation of study drug
16. History of allergic reaction to darolutamide or ipatasertib.
17. Any condition that in the opinion of the investigator would impair the patients' ability to comply with study procedures.

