6. TOXICITIES AND DOSE DELAYS/DOSE MODIFICATIONS

The NCI Common Terminology Criteria for Adverse Events (CTCAE) v5 will be used to grade adverse events.

Subjects enrolled in this study will be evaluated clinically and with standard laboratory tests before and at regular intervals during their participation in this study as specified in Study Calendar & Evaluations.

Subjects will be evaluated for adverse events (all grades), serious adverse events, and adverse events requiring study drug interruption or discontinuation as specified in Study Calendar & Evaluations.

Risks associated with ipatasertib

Hyperglycemia, including cases of Grade 3 or Grade 4 hyperglycemia, has been reported in patients receiving ipatasertib as monotherapy or ipatasertib in combination with other anticancer drugs or hormonal therapy. Hyperglycemia of any grade, regardless of causality, was reported in 35.3% of patients who received ipatasertib as a single agent in the Phase I Study PAM4743g, with Grade 3 hyperglycemia occurring in 1 patient (2.0%). In the GO27983 study, hyperglycemia of any grade, regardless of causality, was reported in 22.6%, 9.1%, and 7.4% of patients in the ipatasertib 400 mg, 200 mg, and placebo arms, respectively. Grade 3 hyperglycemia occurred in 10.7%, 2.3%, and 2.5% of patients in the 400 mg, 200 mg, and placebo arms, respectively. One patient (1.2%) in the ipatasertib

400 mg arm experienced Grade 4 hyperglycemia. There were no other instances of Grade 4 or higher hyperglycemia events in any arm. In the GO29227 study, hyperglycemia of any grade, regardless of causality, was reported in 9.5% and 3.3% of patients in the ipatasertib 400 mg and placebo arms, respectively. There were no reports of Grade ≥ 3 hyperglycemia.

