Rash, primarily manifested as maculo-papular type with or without pruritus, has been commonly reported in patients receiving treatment with ipatasertib. Rash-related events of any grade, regardless of causality, were reported in 15.7% of patients who received ipatasertib as a single agent in the Phase I Study PAM4743g; Grade 3 rash (toxic skin eruption as reported term) was reported in 1 patient (2.0%). In the GO27983 study, irrespective of grade or causality, the proportion of patients experiencing a rash-related event was 23.8%, 9.1%, and 6.2% in the ipatasertib 400 mg, ipatasertib 200 mg, and placebo arms, respectively. Of patients in the ipatasertib 400 mg, 200 mg, and placebo arms, 9.5%, 2.3%, and 0%, experienced Grade 3 rash, respectively. One patient (1.2%) in the ipatasertib 400 mg arm experienced a Grade 4 event. There were no other instances of Grade ≥ 4 events in this study. In the GO29227 study, rash of any grade, regardless of causality, was reported in 30.2% and 30.0% of the ipatasertib 400 mg and placebo arms, respectively. There was 1 patient with Grade 3 rash in each arm (1.6% and 1.7% in the ipatasertib 400 mg and placebo arms, respectively). There were no cases of Grade 4 or Grade 5 rash events in any arm. Cases of Grade 3 rash requiring dose interruption and treatment with topical or systemic corticosteroids have also been observed from other ongoing ipatasertib studies.

Erythema multiforme: In the blinded Study CO39303, erythema multiforme of any grade regardless of causality was reported in 6 (0.5%) patients. Grade 3 erythema multiforme was reported in 5 of these 6 patients. In the blinded Study CO40016, one Grade 3 event of erythema multiforme was reported. An analysis of the first 4 cases of erythema multiforme reported, with a cut off date of 7 June 2018, found that the frequency of reported events of erythema multiforme is 4 out of 1051 patients (0.38%) and is a higher frequency than the reported global incidence rate of 1.2-6 per million. Published literature

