suggests a possible causal association between PI3K inhibitors and erythema multiforme. The first dose latencies ranged from 9-16 days for these four cases, which is consistent with the literature describing drug-induced erythema multiforme. On 1 June 2018 an independent Data Monitoring Committee conducted a review of the totality of the safety data (unblinded), including skin toxicity-related events and details of the four erythema multiforme cases (from Study CO39303), and concluded that Study CO39303 be continued with no modifications to the conduct. Further evaluation and assessment will occur after Studies CO39303 and CO40016 are unblinded.

Fatigue or asthenia of any grade, regardless of causality, has been observed in 62.7% of patients receiving ipatasertib as a single agent in the Phase I Study PAM4743g, with 5 (9.8%) cases of Grade 3 asthenia/fatigue reported. In the GO27983 study, asthenia/fatigue of any grade, irrespective of causality, was reported in 48.8%, 45.5%, and 43.2% of patients in the ipatasertib 400 mg, 200 mg, and placebo arms, respectively. Grade 3 asthenia/fatigue occurred in 9.5%, 5.7%, and 3.7% of patients, respectively, as above. There were no cases of Grade 4 or Grade 5 asthenia/fatigue events in any arm. In the GO29227 study, asthenia/fatigue of any grade, regardless of causality, was reported in 49.2% and 43.3% of the ipatasertib 400 mg and placebo arms, respectively. Grade 3 asthenia/fatigue was reported in 6.3% and 6.7% of the ipatasertib 400 mg and placebo arms, respectively. There were no cases of Grade 4 or Grade 5 asthenia/fatigue events in any arm.

Refer to the Ipatasertib Investigator's Brochure for further information regarding the nonclinical and clinical safety evaluation of ipatasertib as a single agent and in combination with chemotherapy.

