a. Staging may be captured from initial diagnosis.

b. Repeat abdominal imaging to confirm stage must be performed within 90 days of trial initiation.

c. Staging will be based on the 8th edition of the AJCC Cancer Staging Manual.

⁷Vital signs to include blood pressure, weight, and height (screening only) and ECOG performance status

⁸Laboratory assessment will be performed prior to treatment initiation as noted and every cycle thereafter at clinic visits during treatment periods.

⁹CMP to include sodium, potassium, chloride, creatinine, blood urea nitrogen; liver function tests (LFTs) to include AST, ALT, total bilirubin, alkaline phosphatase

¹⁰After Cycle 4, disease assessments will be performed every 12 weeks (+/- 4 weeks) for two years, and then every 16 weeks (+/- 8 weeks).

¹¹Fixed paraffin-embedded blocks/slides will be requested by the investigator enrolling the patient. Request should be placed when the patient is being screened and slides should be shipped by C1D1 of treatment. If available, slides are required for central confirmation of PTEN analysis and other biomarker research. See CLM for collection, labeling, and shipping instructions.

¹²Plasma will be collected on Cycle 1 Day 1 for Ipatasertib monotherapy PKs (pre-dose, +1h, +2h, +3h, +5h). Subjects will begin Darolutamide in the evening of C1D1 AFTER drawing samples for PKs on Ipatasertib. Additional samples will be collected on Cycle 1 Day 15 and Cycle 3 Day 1 (pre-dose, +1h, +2h, +3h, +5h on each day) to evaluate PKs for combination therapy.

¹³Submission of unstained slides for banking from an archived FFPE tumor block (if available). See CLM for collection, labeling, and shipping instructions.

STUDY CALENDAR & EVALUATIONS: PHASE II NEOADJUVANT COHORT

Cycle = 28 days	Screen		Phase II Neoadjuvant Cohort ² (± 3 days)			Surgery ³	Safety follow up ²	Long-term Follow up ⁵	
			Cycles 1-2		Cycles 3-6				
	-90 days	-14 days ¹	Day 1	Days 8, 15	Day 1	Day 29			
REQUIRED ASSESSMENTS									
Medical history, smoking history, trial awareness ⁶	X								
Diagnosis and Staging ⁷	X								
Physical exam, Vital signs, ECOG Performance status ⁸		X	X		X	X		X	
AEs & concomitant medications		X	X		X	X		X	
Immunohistochemistry for PTEN ¹¹	X								
ECG	X								
LABORATORY ASSESSMENTS⁹									
Complete Blood Cell Count with diff (CBC)		X	X		X	X		X	
Comprehensive Metabolic Profile (CMP) ¹⁰		X	X		X	X		X	
HgA1C		X				X		X	
Fasting glucose		X	X	X	X	X		X	

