11.2 Reporting

11.2.1 Adverse Events

- AEs will be recorded from time of signed informed consent until 30 days after discontinuation of study drug(s) or until a new anti-cancer treatment starts, whichever occurs first.
- AEs will be recorded regardless of whether or not they are considered related to the study drug(s).
- All AEs will be recorded in the subject's medical record and on the appropriate study specific eCRF form within the EDC system.
- All AEs considered related to study drug(s) will be followed until resolution to \leq Grade 1 or baseline, deemed clinically insignificant, and/or until a new anti-cancer treatment starts, whichever occurs first.

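### Lipids are an entry limit and a selected adverse event in both cohorts, but neither study calendar schedules a lipid test

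*Combined protocol and SAP*

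**What the plan says.** **Entry.** Section 3.2.2 item 12 excludes men with Grade 2 or higher "uncontrolled or untreated hypercholesterolemia (>300 mg/dL) or hypertriglyceridemia (>300 mg/dL". Section 3.1.2 item 9 sets the same limits for Phase I.

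**Collection.** Section 11.1.6 lists "Hyperlipidemia (hypercholesterolemia, hypertriglyceridemia, hyperlipidemia, blood cholesterol increased, blood triglycerides increased" and introduces its list with "Additional data including grade, timing and required interventions will be collected for the following selected adverse events".

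**Measurement.** Neither calendar in Section 7 names cholesterol, triglycerides or a lipid panel. The metabolic panel is defined in footnote 9 (Phase I) and footnote 10 (Phase II) as electrolytes, creatinine, urea nitrogen and liver tests. The organ-function tables in 3.1.1 item 12 and 3.2.1 item 13 contain no lipid value.

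**What counts as an adverse event.** Under 11.1.1 an abnormal laboratory value is an adverse event only if it causes signs or symptoms, or needs treatment or further testing.

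**Timing of adverse event review.** Section 6 says that men will be evaluated for all adverse events, including "adverse events requiring study drug interruption or discontinuation as specified in Study Calendar & Evaluations". In the Phase II calendar the row "AEs & concomitant medications" is marked on Day 1 of each cycle and is blank under Days 8 and 15 of Cycles 1-2.

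**The concern.** The plan screens out a laboratory abnormality and undertakes to describe the same abnormality on treatment, but requires nobody to measure it. Two things follow.

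First, whether a man meets the exclusion depends on what happens to be in his record. A man with no recent lipid result can be enrolled with values above the limit, and neither the site nor a monitor could show otherwise.

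Second, toxicity is a secondary objective and 12.6.2 promises descriptive rates. A lipid rise may cause no symptoms. Without a scheduled test, the reported count depends on who was tested for some other reason. Without a baseline value, a raised result on treatment cannot be told apart from one present at entry.

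**Working it through.** The main check sets the sections side by side; the arithmetic is counting.

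1. **Scheduled lipid tests.** The Phase I calendar has seven laboratory rows: blood count, metabolic panel, HbA1c with LDH, fasting glucose, testosterone, PSA, and hepatitis/HIV antibodies. The Phase II calendar has five: blood count, metabolic panel, HbA1c, fasting glucose, and testosterone with PSA. Lipid rows: 0 of 7 and 0 of 5. Total enrolment is 6-18 plus 20, or 26-38 men, so scheduled lipid measurements are 0 x 26 to 0 x 38 = 0.

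2. **Is the omission deliberate?** Other measured entry limits have a matching calendar row: HbA1c, fasting glucose, creatinine, bilirubin and transaminases, and an ECG for the QTcF limit. Where the plan waives testing it says so, as in the viral-infection note in 3.2.2 item 5. Lipids have no such waiver.

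3. **What a reported rate would mean.** Expected reported proportion = true proportion x probability of being tested x probability that the result then qualifies under 11.1.1. The plan fixes neither of the last two factors. To illustrate with 20 Phase II men: if all were tested and none was raised, the exact two-sided 95% upper limit would be 1 - 0.025^(1/20) = 16.8%. If testing is left to chance, 0 of 20 gives no such bound.

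4. **Fasting samples already scheduled.** Phase II: screening 1 + Day 1 of Cycles 1-2, 2 + Days 8 and 15 of Cycles 1-2, 2 x 2 = 4 + Day 1 of Cycles 3-6, 4 + the Day 29 column, read as one end-of-treatment draw, 1 + safety follow-up 1 = 13 per man. Phase I through Cycle 4: screening 1 + Cycle 0 Day 1, 1 + Cycle 1 Days 1 and 15, 2 + Day 1 of Cycles 2-4, 3 = 7 per man. Footnote 1 may save one repeat. Phase I safety follow-up has no fasting sample marked.

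5. **Phase II adverse event review.** Cycle 1 Day 1 is study day 1. The next marked review is Cycle 2 Day 1: 1 + 28 = day 29, or 26-32 with the 3-day window. On Days 8 and 15 fasting glucose is the only assessment marked.

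6. **Scale of the erythema multiforme text in Section 6.** The plan states that the frequency of "erythema multiforme is 4 out of 1051 patients (0.38"%. Check: 4/1051 = 0.381%, which reproduces. Section 6 also gives 0.5% (6 patients in one study). Expected cases in 20 men: 20 x 0.0038 = 0.08 to 20 x 0.005 = 0.10. Chance of at least one: 1 - (1 - 0.00381)^20 = 7.3% to 1 - 0.995^20 = 9.5%.

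7. **The Phase I clock.** Cycle 0 is 7 days of ipatasertib alone. Adverse event checks therefore fall on ipatasertib day 1, day 8 (Cycle 1 Day 1), day 7 + 15 = 22 (Cycle 1 Day 15) and day 7 + 29 = 36 (Cycle 2 Day 1).

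**The case against.** **On lipids.** The exclusion concerns known uncontrolled or untreated disease, and a site can apply it from the medical history or from results already on file. Section 11.1.6 can be read as saying what to collect once an event occurs, not as promising a test. Hyperlipidemia is not an event of special interest in 11.1.5, is absent from the ipatasertib risk text in Section 6, and has no management table in 6.3.1. Under 11.2.1, "AEs will be recorded from time of signed informed consent until 30 days after discontinuation of study drug(s"), and 14.2 allows standard-of-care data to be captured. Nor would assays alone give a clean adverse event rate, because of the definition in 11.1.1.

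Much of this stands. It limits the importance of the gap and rules out saying that the exclusion is unusable. It does not supply a required measurement, and the last argument is a reason to keep the values as laboratory data.

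**On early review.** A reader might infer that Phase II leaves men unreviewed through a known risk window for erythema multiforme, and that Phase I shows the proper schedule. The documents do not support this.

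- Section 6 says "The first dose latencies ranged from 9-16 days for these four cases". That is an observed range from four cases in another, then blinded, study, whose monitoring committee let it continue unmodified. It is not a defined risk period, and about 0.1 cases are expected in 20 men.
- Phase I is not a contrast: none of its nominal checks falls on ipatasertib days 9-16 either.
- The Grade 3 diarrhea and rash percentages in Section 6 cannot size the gap. They are whole-study rates from other trials at 400 mg, and no split by time is given.
- Men are told to report diarrhea early, and the interruption rules in 6.3.1 are triggered by events, not by visits.
- Phase II footnote 2 sets visits every 28 days, so Days 8 and 15 may be laboratory draws without an examiner.

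What survives is narrow: men attend on two days per cycle in Cycles 1-2 with no adverse event question marked, although several interruption rules depend on grading.

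**Conclusion.** The lipid inconsistency holds. Three parts of the plan do not fit together: the exclusion criteria, the selected event list and the calendars. Scheduled lipid measurements number zero across 26-38 men, so the exclusion cannot be verified from required tests and any reported hyperlipidemia rate would be uninterpretable.

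A reader might go further and infer that untreated men will certainly be enrolled, that rises will never be seen, or that the reported rate will be near zero. The documents give no lipid event rate, and history, existing results and unscheduled testing all remain possible, so none of these follows.

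The Phase II review gap, from study day 1 to day 29, is real but secondary and minor. Loss of Grade 3-4 events from the toxicity endpoint is not shown, since symptomatic events can still be recorded at day 29.

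Both matters concern safety ascertainment. The primary endpoint, sample size and stopping rules are unaffected. The conclusion assumes that the calendars list all required tests, and that no lipid test is required in a manual or case report form outside these documents.

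**What to change.** 1. Add total cholesterol and triglycerides to the fasting sample already drawn at screening in both cohorts, and to chosen fasting samples already scheduled on treatment in both calendars. Phase I safety follow-up has no fasting sample marked, so it should not be assumed to provide one.
2. Record the values as laboratory data whether or not they meet the adverse event definition in 11.1.1, and summarise them with the number of men tested as denominator.
3. If the sponsor intends no lipid testing, say so, as the plan does for viral infections, and state how the exclusion and the selected event will be ascertained.
4. Reconcile the Phase II review schedule with the early-onset toxicity text in Section 6 and the grade-based interruption rules in 6.3.1, for example by marking the existing adverse event and concomitant medication row at the Day 8 and Day 15 contacts. How to monitor clinically is for the sponsor to decide.

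**Cost.** The lipid change is a calendar edit and a small assay charge, with no new visits or draws. Item 4 adds some staff time if those contacts are laboratory-only, and may add some low-grade events to the record.
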